# 9.2 Stage III, IV ENKTL

Newly diagnosed patients with advanced stage disease will obtain baseline FDG-PET/CT simulation after a Radiation Oncology consultation. They will initially receive 2 cycles of single-agent pembrolizumab, 200mg IVPB every 3 weeks followed by reassessment by PET. Patients with no evidence of disease progression will receive another 2 cycles of pembrolizumab. In addition, patients with an "indeterminant response" by the LYRIC criteria (evidence of disease progression on PET but with clinical improvement) can be considered for another 2 cycles of pembrolizumab after discussion with the MSK PI. After 4 cycles of pembrolizumab, those who achieve a partial metabolic response (PMR) to pembrolizumab will proceed to 3 cycles of SMILE chemotherapy, up to 50.4 Gy of involved site radiation therapy (if determined to be appropriate by a Radiation Oncology Attending and according to institutional standards), followed by 10 months maintenance therapy with pembrolizumab. Patients who do not achieve partial metabolic response to pembrolizumab will undergo biopsy. Those with biopsy showing evidence of lymphoma will come off study and receive treatment per discretion of treating physician. If the biopsy shows no evidence of lymphoma, patients will receive the same treatment as those with PMR.

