# 9.0 TREATMENT/INTERVENTION PLAN

#### 9.1 Stage I, II ENKTL

Newly diagnosed patients with early stage disease will initially receive the following study treatment:

- Baseline FDG-PET/CT simulation will be done following an initial consultation in Radiation Oncology (main center) and prior to starting therapy
- 2 cycles of single-agent pembrolizumab, 200mg IVPB every 3 weeks
- Reassessment by PET after 2 cycles of pembrolizumab
  - o If no evidence of disease progression, another 2 cycles of pembrolizumab.
  - Patients with an "indeterminant response" by the LYRIC criteria (evidence of disease progression on PET but with clinical improvement) can be considered for another 2 cycles of pembrolizumab after discussion with the MSK PI.
  - Patients with progression of disease without evidence of clinical improvement will proceed to 2 cycles of SMILE chemotherapy and ISRT.
  - Patients who progress to stage III or IV ENKTL will come off treatment and receive subsequent standard of care treatment at the discretion of the treating physician.
- Reassessment by PET after 4 cycles of pembrolizumab
  - If CR response on PET, patients will begin 45 Gy of involved site radiation (ISRT) and an additional 6 months of maintenance pembrolizumab. ISRT will begin 2-6 weeks after cycle 4 of pembrolizumab.
  - Patients with less than CR will undergo a biopsy. If biopsy shows no evidence of lymphoma, patients will proceed with same treatment as those with PET CR.

 Patients with less than complete response by PET and persistent evidence of disease on biopsy after 4 cycles of pembrolizumab will proceed to 2 cycles of SMILE chemotherapy and ISRT.

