- 15. **Pembrolizumab**: Pembrolizumab is administered every 3 weeks (21 days) on Day 1 of each cycle, ± 3 days. Pembrolizumab is given 200m via IVPB infusion over 30 minutes (+/- 5 minutes).
- 16. **Reassessment by PET after 4 Cycles of pembrolizumab**: If Partial Metabolic Response (PMR) by PET, patients may begin 45 Gy of involved site radiation (ISRT) if indicated, and an additional 6 months (8 cycles) of maintenance pembrolizumab. ISRT will begin 2-6 weeks after Cycle 4 of pembrolizumab. Patients with less than PMR will undergo a biopsy. If biopsy shows no evidence of lymphoma, patients will proceed with same treatment as those with PET CR. Patients with less than PMR by PET and persistent evidence of disease on biopsy after 4 cycles of pembro will be taken off study.
- 17. **Follow-up** includes: standard clinic visit and laboratory tests (CBC, comp only). EBV PCR every 3 months for 3 years. Imaging to be obtained every 6 months for 2 years post treatment. cfDNA to be collected 6 months, 1 year, and 2 years into follow up or until a new therapy is initiated.
- 18. PET/CT to be completed at baseline only if the patient will not be receiving radiation therapy.
- 19. Patients will be followed by PET/CT (skull apex to midthigh) If PET/CT is not feasible, patients may be followed with CT CAP plus CT nasal cavity (for patients with nasal cavity disease) after discussion with MSK PI. If followed by PET/CT, additional diagnostic CT is NOT required.
- 20. PET/CT to be done after last cycle of SMILE only may be done prior to treatment on C5D1. All other assessments marked should be done for every cycle of SMILE.
- 21. cfDNA to be collected at C1D1, C4D1, C5D1 of pembrolizumab, end of treatment, and 6 months, 1 year, and 2 years into follow up or until a new therapy is initiated.

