Partial	Partial metabolic response	Partial remission (all of the following)
Lymph nodes and extralymphatic sites	Score 4 or 51 with reduced uptake compared with baseline and residual mass(es) of any size	≥ 50% decrease in SPD of up to 6 target measurable nod and extranodal sites
	At interim, these findings suggest responding disease	When a lesion is too small to measure on CT, assign 5 mm × 5 mm as the default value
	At end of treatment, these findings indicate residual disease	When no longer visible, 0 × 0 mm
		For a node > 5 mm × 5 mm, but smaller than normal, use actual measurement for calculation
Nonmeasured lesions	Not applicable	Absent/normal, regressed, but no increase
Organ enlargement	Not applicable	Spleen must have regressed by > 50% in length beyond normal
New lesions	None	None
Bone marrow	Residual uptake higher than uptake in normal marrow but reduced compared with baseline (diffuse uptake compatible with reactive changes from chemotherapy allowed). If there are persistent focal changes in the marrow in the context of a nodal response, consideration should be given to further evaluation with MRI or biopsy or an interval scan	Not applicable
No response or stable disease	No metabolic response	Stable disease
Target nodes/nodal masses, extranodal lesions	Score 4 or 5 with no significant change in FDG uptake from baseline at interim or end of treatment	< 50% decrease from baseline in SPD of up to 6 dominar measurable nodes and extranodal sites; no criteria for progressive disease are met
Nonmeasured lesions	Not applicable	No increase consistent with progression
Organ enlargement	Not applicable	No increase consistent with progression
New lesions	None	None
Bone marrow	No change from baseline	Not applicable
Progressive disease	Progressive metabolic disease	Progressive disease requires at least 1 of the following
Individual target nodes/nodal masses	Score 4 or 5 with an increase in intensity of uptake from baseline and/or	PPD progression:

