#### CRITERIA FOR REMOVAL FROM STUDY 13.0

Patients will be followed on study until progression of disease or 2 years following completion of study treatment.

The following patients will be removed from study:

- Patients whose treating physicians determine that it is in their best interest to be removed from the study.
- Patients who develop unacceptable toxicity.
- Patients who request that they be removed from study. This will not compromise the care they receive at this institution.
- Patients who are non-compliant with treatment or follow-up.

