### **Secondary objectives:**

The secondary objectives of the study are safety of the treatment program, overall response rate (ORR) and partial metabolic response (PMR) rate to pembrolizumab, progression free survival (PFS), and overall survival (OS). Adverse events related to treatment will be tabulated and analyzed using descriptive statistics. ORR and PMR rates will be assessed after 4 cycles of pembrolizumab and calculated along with an exact 95% confidence interval. Progression free survival (PFS) and overall survival (OS) will be calculated using the method of Kaplan-Meier. Time origin for PFS and OS are time of treatment initiation. PFS and OS will be analyzed separately for early and advanced stage patients.

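### Advanced-stage patients taken off study after cycle 4 with persistent lymphoma but no progression have no stated follow-up and no PFS rule; if they are censored, 2-year PFS would probably be overstated

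*Combined protocol and SAP*

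**What the plan says.** All references are to the combined protocol and SAP.

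- **Off-study rule.** For stage III–IV patients below PMR after cycle 4, Section 9.2 states: "Those with biopsy showing evidence of lymphoma will come off study and receive treatment per discretion of treating physician". Section 4.2 has the same rule, and footnote 16 of the stage III–IV calendar (Section 10.2) repeats it: "Patients with less than PMR by PET and persistent evidence of disease on biopsy after 4 cycles of pembro will be taken off study".
- **Response categories.** The Lugano response table in Section 12.0 keeps no metabolic response separate from progression, describing it as "Score 4 or 5 with no significant change in FDG uptake from baseline at interim or end of treatment". The text of Section 12.0 also requires an SUV reduction of at least 30% for PMR.
- **Early stage.** In Section 9.1, stage I–II patients with less than a complete response on PET and "persistent evidence of disease on biopsy after 4 cycles of pembrolizumab will proceed to 2 cycles of SMILE chemotherapy and ISRT".
- **Follow-up.** Section 13.0 says: "Patients will be followed on study until progression of disease or 2 years following completion of study treatment". Nothing describes follow-up for progression once a patient is off study.
- **PFS analysis.** Under secondary objectives, Section 14.0 names the estimator: "Progression free survival (PFS) and overall survival (OS) will be calculated using the method of Kaplan-Meier". It counts both times from the start of treatment, and on the split by stage it adds: "PFS and OS will be analyzed separately for early and advanced stage patients". It does not define a PFS event or give a censoring rule.

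**The concern.** Being below PMR is not the same as progressing. A patient whose uptake is unchanged, or has fallen by less than 30%, has neither reached PMR nor progressed. If the biopsy still shows lymphoma, the off-study rule ends observation without a recorded PFS event.

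The usual PFS definition counts progression or death. Under it, a Kaplan-Meier analysis would censor that patient at the last assessment. Kaplan-Meier assumes that censored patients have the same outlook as those still at risk. Here the reason for leaving is biopsy-proven failure of the study drug, so the assumption is doubtful and the censoring is probably informative.

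Early-stage patients with persistent disease on biopsy continue to further protocol treatment, and their later progressions can be counted. The two stage-specific curves could therefore handle a similar finding differently.

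Two-year PFS is a named secondary objective. Section 3.0 reports 18% for advanced-stage patients at the institution and identifies this group as the one in which efficacy most needs to improve. A reader is likely to look at the new figure with that one in mind.

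**Working it through.** **The plan's own figures.** The documents give no PFS precision, event count or power, so there is no PFS figure to reproduce. The only design figure is the interval for the complete response rate: 0.40 ± 1.96 × √(0.40 × 0.60 / 19) = 0.40 ± 0.220, or 0.18 to 0.62. It agrees with Section 14.0 but does not bear on PFS.

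**Who is affected.** Three groups can be below PMR after cycle 4:

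| Status after cycle 4 | Biopsy | PFS status under progression or death |
|---|---|---|
| Progressive metabolic disease | any | Event |
| Not PMR, not progression | no lymphoma | Stays on study, treated as PMR |
| Not PMR, not progression | lymphoma | Off study, no event recorded |

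Only the third row is at issue. It is a foreseeable group, because Section 9.2 continues patients past cycle 2 when they have not progressed.

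**Timing.** Cycles last 21 days and the PET falls on days 14–21 of cycle 4. Counting from the first dose, that is between 63 + 14 = 77 and 63 + 21 = 84 days, or about week 11 to 12.

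**Number of advanced-stage patients.** Section 14.0 plans 19 patients and expects 66% to be early stage, so 19 × 0.34 = 6.5, or six to seven patients.

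**Formula.** Let N be the number of advanced-stage patients, e the progressions before the cycle 4 assessment, k the patients removed as in the third row, and s the patients known to be progression-free at 2 years.

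- Removed patients counted as events: S = s / N.
- Removed patients censored: S = ((N − e) / N) × s / (N − e − k).

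The documents do not give e, k or s, so the values below are assumptions. The comparison with s / N also assumes that every removed patient progresses within 2 years. It takes s = 1, because 1/6 is close to the historical 18%.

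| N | e | k | Counted as events | Censored |
|---|---|---|---|---|
| 6 | 0 | 0 | 1/6 = 16.7% | 16.7% |
| 6 | 0 | 1 | 16.7% | 1/5 = 20.0% |
| 6 | 0 | 2 | 16.7% | 1/4 = 25.0% |
| 6 | 0 | 3 | 16.7% | 1/3 = 33.3% |
| 6 | 1 | 2 | 16.7% | (5/6) × (1/3) = 27.8% |
| 7 | 0 | 1 | 1/7 = 14.3% | 1/6 = 16.7% |
| 7 | 0 | 3 | 14.3% | 1/4 = 25.0% |

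**Large-sample version.** If PFS with removed patients counted as events is 18% and nobody progresses earlier, censoring a share f gives 0.18 / (1 − f). That is 20.0% for f = 0.1, 22.5% for 0.2, 25.7% for 0.3 and 30.0% for 0.4.

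**Direction.** Compared with counting removals as failures, censoring raises the estimate whenever k and s are both above zero. Compared with the patients' real progression times, it raises the estimate only if they do worse than those who stay. With N = 6, e = 0 and k = 2, censoring credits the removed patients with the 1/4 success rate of the four who remain. If one of the two were in fact progression-free at 2 years, the true value would be 2/6 = 33.3%, above the censored 25.0%. Worse outcomes are likely after biopsy-proven failure, but the documents do not give them.

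**Sampling error.** The exact 95% confidence interval for 1/6 is 0.4% to 64.1%.

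**The case against.** A reader might infer that the plan censors these patients and that advanced-stage PFS is therefore biased upward. The documents do not say so. Section 14.0 is silent, and an analyst could count persistent lymphoma on biopsy, or the start of new therapy, as an event. The upward bias would then disappear. This objection stands, and it is why the point is conditional. It does not remove the problem: without a rule, the choice would be made after the data are seen, and the off-study rule may leave no later progression dates to use.

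A reader might also infer that the curve would rest mainly on responders, or that the rate would be inflated 1.5 to 2 times. Neither is supported. Progressors remain events, and those ratios need two or three of six patients to be removed. With one removed the ratio is 20.0 / 16.7 = 1.2, and with none there is no effect. The protocol's expectations (all seven relapsed or refractory patients responding, and a complete response rate of at least 40%) suggest that few would be removed.

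Three further points are fair:

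- Section 13.0 does not list persistent disease without progression as a reason for removal, so loss of follow-up is partly an inference. But Sections 4.2, 9.2 and 10.2 all say off study, while Section 9.1 uses a separate expression for leaving treatment. The tension needs resolving.
- In a 19-patient pilot, sampling error is much larger than the shift. That is true, but a confidence interval does not reveal informative censoring.
- No formal comparison with 18%, or between stages, is planned. This limits the consequence of the gap, although the 2-year PFS estimate is still to be reported.

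**Conclusion.** The point holds in conditional form. A stated rule ends observation of some advanced-stage patients because study treatment has failed, without a progression event. No later follow-up is described, and no PFS event or censoring rule covers them. If they are censored, as they would be under the usual PFS definition, advanced-stage 2-year PFS would probably be overstated.

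The number affected is unknown. For six patients and zero to three removals, under the assumptions shown, the estimate runs from 16.7% to 33.3%, well inside the sampling uncertainty. The upward direction also assumes that removed patients do worse than those who stay.

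The primary endpoint is not touched: these patients have been assessed and count as not in complete response. The gap should be closed because it concerns data for a named secondary objective that may be hard to recover later.

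**What to change.** None of these changes alters treatment.

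1. In Sections 4.2 and 9.2 and in footnote 16 of the stage III–IV calendar, reword so that these patients come off *study treatment*, not off *study*. Reconcile this with the follow-up rule and removal list in Section 13.0.
2. For these patients, keep collecting the dates of progression, next lymphoma therapy and death from routine records.
3. In Section 14.0, define PFS as time from treatment initiation to documented progression or death, regardless of leaving study treatment, and state the censoring rule.
4. Add a sensitivity analysis that counts removal with biopsy-proven lymphoma as an event on the removal date.
5. Report how many patients were removed this way.

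The cost is a wording amendment and chart review for a few patients. The reported advanced-stage PFS may be lower.

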#### 9.3 Pembrolizumab

# **Dosing**

Dosing of pembrolizumab is outlined in Table 3.0 below. Pembrolizumab will be administered every 3 weeks (21 days) (+/-3 days).

**Table 3.0 Pembrolizumab Dosing** 

Drug	Dose/Potency	Route of Administration	Regimen/Treatment Period
Pembrolizumab	200mg Flat	IVPB over 30 minutes	Once every 21 days

#### Administration

Pembrolizumab should be administered on Day 1 of each cycle after all procedures/assessments have been completed as detailed on the Schedule of Assessments (Section 10.0). Study treatments will be administered on an outpatient basis. Study treatment may be administered up to 3 days before or after (+/- 3 days) the scheduled Day 1 of each cycle. Subjects may be dosed with pembrolizumab no less than 17 days from the previous dose. Treatment related toxicity requiring treatment delay of 6 weeks or more would require removal from the study unless after discussion with the PI it is felt to be clinically appropriate for the patient to remain on study.

# **Supportive Care/Premedications**

There are no premedications routinely recommended unless patient has experienced previous infusion reaction. Subjects should be carefully monitored for infusion reactions during pembrolizumab administration. If an acute infusion reaction is noted, subjects should be managed according to 7.0 in Section 11.6.

Dose modifications of Pembrolizumab are discussed in Section 11.5.

# **9.4 SMILE**

The SMILE regimen will be administered as per institutional guidelines and is outlined in the table below. SMILE will begin at the discretion of the treating physician following the last dose of pembrolizumab and is administered every 21-28 days.

# Table 4 SMILE regimen

Drug	Dose/Potency	Route of Administration	Regimen/Treatment Period
Methotrexate	2000 mg/m2	IVPB over 6 hours	Day 1
Leucovorin	25mg FLAT	IVPB q 6 hours	Begin 30 hours after start of Methotrexate
Ifosfamide	1500mg/m2	IVPB over 1 hour	Days 2, 3, 4
MESNA	300mg/m2	IVPB over 15 min	30 min prior to chemo, then 4 and 8 hours post chemo
Etoposide	100mg/m2	IVPB over 1 hour	Days 2, 3, 4
Dexamethasone	40mg	IVPB	Days 2, 3, 4
PEG-asparaginase	1500-2000 units/m2	IM or IVPB over 1 hour	Between day 5 and 8
Pegfilgrastim	6mg	SC	Between day 5 and 8

#### 9.5 Involved site radiation

Patients with stage I or II disease will undergo involved site radiation therapy (ISRT) according to published ILROG guidelines for using ISRT for extranodal lymphomas.  A total dose of 45 Gy (25 daily treatments) will be given with the option of increasing it to 50.4 Gy (28 daily treatments) for patients who have PET-positive disease after pembrolizumab. Involved site radiation therapy will begin 2-6 weeks following cycle 4 of pembrolizumab. Cycle 5 of pembrolizumab will begin 3-6 weeks following completion of radiation. Patients with advanced stage disease may receive ISRT if indicated. ISRT may be administered between cycles of SMILE or after SMILE and will be performed according to institutional standards.

# 10.0 EVALUATION DURING TREATMENT/INTERVENTION

# 10.1 Evaluations during treatment for stage I, II patients:

# Study Calendar, Stage I, II

Assessment Period	Screening 	Сус	le 1	Сус	le 2	ıf	Cycle 3	Сус	cle 4	In	Cycles 5	- Cycle 12	Post-Trea	atment
Study Days	Day -28 to 1	Day 1	Day 8-20	Day 1	Day 14- 21	PD	Day 1	Day 1	Day 14-21	volve		Day 14-21	End of Treatment	Follow up 
Visit Window 	-28 days	- 3 days		+/- 3 days		with n mothe	+/- 3 days	+/- 3 days	+/- 3 days	d Site				+/- 1 month
Informed consent	Х					no c erap				R				
Medical History	Х					< =				adi				
Review of concomitant medications		Х		Х		nical i and IS	Х	Х		ation	Х		Х	
Review of adverse events		Х		Х		l imp	Х	Х		Τh	Х		Х	
Physical Examination 		Х		Х		(Involved footnote	Х	Х		O O	Х		Х	Х
Vital Signs 		Х		Х		em lvo	Х	Х		rapy (ISF footnote	Х		Х	Х
ECOG/KPS		Х		Х		len lve	Х	Х		ot (E	Х		Х	Х
Hematology  and Chemistry 		Х		Х		t, proc d Site e 16]	Х	Х		7T)			Х	Х
HIV, Hepatitis B and Hepatitis C 	х					ᄁᅋ				OR SI				
Pregnancy test 8		Х				ed to 2 adiatio				 				
EBV PCR 9		Х		Х		2 c ion		Х		'n	Х		Х	Х
Referral to radiation oncology	х					ycles of Therapy				then				
FDG-PET/CT simulation 	Х					s of				ISR				
MRI nasal cavity (only for patients with nasal cavity disease)	х					SMILE y (see				T [see				
ECHO	Х													

ECG	Х											
Pulmonary function tests 11	Χ											
Baseline Biopsy or archive tissue 12	Х											
Research Tumor Biopsy 13			Х					X 				
PET/CT	X 				Х			Х		Cycle 8 & Cycle 12 	X	Х
Tumor assessment 14					Х			Х		Cycle 8 & Cycle 12		
cfDNA 		Х					Х		Х		Х	X 
Pembrolizumab 		Х		Х		Х	Х		Х			

- 1. Each cycle is 21 days in length.
- 2. **Screening assessments** must be completed prior to initiation of treatment. HIV, Hep B and C tests must be done within 6 months of start of treatment. Baseline biopsy must be done prior to treatment. All other assessments must be done within 28 days of treatment, except for laboratory tests which must be done within 14 days of treatment. Lab tests CBC and comp must be repeated within 3 days of C1D1. Pregnancy test is required for females of child-bearing potential and must be done within 7 days of initiating treatment.
- 3. Physical Examination must include height and weight. The patient's weight in kilograms must be determined before the start of each cycle.
- 4. Vital signs include: pulse, blood pressure, temperature, respiratory rate, and oxygen saturation.
- 5. **Hematology** must include CBC with differentials. Screening CBC done within 14 days of start of treatment. Must be repeated within 3 days of C1D1.
- 6. **Chemistry** must include comprehensive metabolic panel (albumin, alkaline phosphatase, total bilirubin, bicarbonate, BUN, calcium, chloride, creatinine, glucose, potassium, total protein, SGOT [AST], SGPT [ALT], sodium) magnesium, phosphorus amylase, lipase, thyroid function tests (fT4, and TSH) and LDH. Screening comp done within 14 days of start of treatment. Must be repeated within 3 days of C1D1. Screening magnesium, phosphorus, amylase, lipase, thyroid function tests (fT4 and TSH) and LDH must be done within 7 days of starting treatment.
- 7. **HIV, Hep B and Hep C tests** include: HIV I/II antibodies, Hepatitis B surface antigen, core antibody and Hepatitis C antibody. Must be done within 6 months of initiating treatment.
- 8. **Pregnancy test** includes: serum β-HCG or urine pregnancy test for women of child-bearing potential. If the urine test is positive or cannot be confirmed as negative, a serum pregnancy test will be required. Screening pregnancy tests must be performed within 7 days of starting treatment.
- 9. **EBV PCR:** screening EBV PCR must be done within 7 days of starting treatment. It is done on Cycle 2 Day 1, Cycle 4 Day 1, then odd cycles only starting in Cycle 5.
- 10. **Baseline FDG-PET/CT** simulation will be done following an initial consultation in Radiation Oncology and prior to starting therapy. Only required for patients who will be receiving radiation therapy.
- 11. **Pulmonary Function tests** include: DLCO at minimum.
- 12. **Baseline tumor biopsy:** all study participants will be required to have a biopsy that confirms extranodal NK/T cell lymphoma. If a biopsy is already done, 20 unstained slides from archived tissue will be requested for correlative studies if possible. The biopsy must be done prior to initiation of treatment.
- 13. **Research biopsies:** on-treatment biopsies are mandatory for all study participants. Biopsies will be done Cycle 1 (between days 8-20), and Cycle 4 (between days 8-20), except in cases where due to the location of disease, biopsy would be associated with unnecessary risk to the patient.

- 14. Tumor Assessment: is the response assessment after PET scans. Refer to Section 12.0 Criteria for Therapeutic Response/Outcome Assessment.
- 15. **Pembrolizumab**: Pembrolizumab is administered every 3 weeks (21 days) on Day 1 of each cycle, ± 3 days. Pembrolizumab is given 200m via IVPB infusion over 30 minutes (+/- 5 minutes).
- 16. **Reassessment by PET after 2 Cycles of pembrolizumab:** If there is no evidence of disease progression, participant will receive another 2 cycles of pembro. If evidence of disease progression on PET but with clinical improvement, participant can be considered for another 2 cycles of pembro after discussion with the study PI. Patients with progression of disease without evidence of clinical improvement will proceed to 2 cycles of SMILE chemotherapy and ISRT.
- 17. **Reassessment by PET after 4 Cycles of pembrolizumab**: If Complete Response (CR) by PET, patients will begin 45 Gy of involved site radiation (ISRT), and an additional 6 months (8 cycles) of maintenance pembrolizumab. ISRT will begin 2-6 weeks after Cycle 4 of pembrolizumab. Patients with less than CR will undergo a biopsy. If biopsy shows no evidence of lymphoma, patients will proceed with same treatment as those with PET CR. Patients with less than CR by PET and persistent evidence of disease on biopsy after 4 cycles of pembro will proceed to 2 cycles of SMILE chemotherapy and ISRT.
- 18. **Follow-up** includes: standard clinic visit and laboratory tests (CBC, comp only). EBV PCR every 3 months for 3 years. Imaging to be obtained every 6 months for 2 years post treatment. cfDNA to be collected 6 months, 1 year, and 2 years into follow up or until a new therapy is initiated.
- 19. PET/CT to be completed at baseline only if the patient will not be receiving radiation therapy.
- 20. Patients will be followed by PET/CT (skull apex to midthigh). If PET/CT is not feasible, patients may be followed with CT CAP plus CT nasal cavity (for patients with nasal cavity disease) after discussion with MSK PI. If followed by PET/CT, additional diagnostic CT is NOT required.
- 21. cfDNA to be collected at C1D1, C4D1, after SMILE or at C5D1 of pembrolizumab, end of treatment, and 6 months, 1 year, and 2 years into follow up or until a new therapy is initiated.

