#### Likely:

Decrease in function of the thyroid gland (if thyroid is in the ISRT field) Transient odynophagia

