#### 17.2.2 Events of Clinical Interest

Selected non-serious and serious adverse events are also known as Events of Clinical Interest (ECI) and must be reported within 2 working days to Merck Global Safety. (Attn: Worldwide Product Safety; [contact]).

For the time period beginning when the consent form is signed until treatment allocation/randomization, any ECI, or follow up to an ECI, that occurs to any participant must be reported within 2 working days to Merck Global Safety if it causes the participant to be excluded from the trial, or is the result of a protocol-specified intervention, including but not limited to washout or discontinuation of usual therapy, diet, placebo treatment or a procedure.

For the time period beginning at treatment allocation/randomization through 90 days following cessation of treatment, or 30 days following cessation of treatment if the participant initiates new anticancer therapy, whichever is earlier, any ECI, or follow up to an ECI, whether or not related to Merck product, must be reported within 2 working days to Merck Global Safety.

Events of clinical interest for this trial include:

- 1. an overdose of Merck product, as defined in Section 17.2.3 Definition of an Overdose for This Protocol and Reporting of Overdose to the Sponsor, that is not associated with clinical symptoms or abnormal laboratory results.
- 2. an elevated AST or ALT lab value that is greater than or equal to 3X the upper limit of normal and an elevated total bilirubin lab value that is greater than or equal to 2X the upper limit of normal and, at the same time, an alkaline phosphatase lab value that is less than 2X the upper limit of normal, as determined by way of protocol-specified laboratory testing or unscheduled laboratory testing.\*

\*Note: These criteria are based upon available regulatory guidance documents. The purpose of the criteria is to specify a threshold of abnormal hepatic tests that may require an additional evaluation for an underlying etiology.

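### As extracted, the stage I-II calendar schedules no hematology or chemistry in maintenance Cycles 5-12, while the stage III-IV calendar does and the protocol's laboratory-based safety rules need the values

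*Combined protocol and SAP*

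**What the plan says.** The stage I-II calendar in Section 10.1 has a row labelled "Hematology 5 and Chemistry 6". As extracted, it is marked on Day 1 of Cycles 1, 2, 3 and 4, at end of treatment and at follow-up. Both cells for Cycles 5-12 are empty. In the first of those two columns, concomitant medications, adverse events, physical examination, vital signs, ECOG/KPS and EBV PCR are marked, and so is pembrolizumab.

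Footnote 17 describes this phase as "an additional 6 months (8 cycles) of maintenance pembrolizumab", and footnote 1 says "Each cycle is 21 days in length". Footnote 6 defines the chemistry panel, which includes liver enzymes, bilirubin, creatinine, glucose and "thyroid function tests (fT4, and TSH) and LDH. Screening comp done within 14 days of start of treatment". Footnotes 5 and 6 give timing only for screening and Cycle 1 Day 1.

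The stage III-IV calendar in Section 10.2 marks the same row for Cycles 5-16 Day 1. Section 9.3 (Administration) has pembrolizumab given on Day 1 of each cycle "after all procedures/assessments have been completed as detailed on the Schedule of Assessments (Section 10.0").

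**The concern.** Section 9.3 makes the calendar the list of what is done before each dose. A site that follows the stage I-II calendar literally would give every maintenance dose without a scheduled blood draw.

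Several safety provisions need laboratory values:

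- Table 6 grades liver toxicity on AST, ALT and bilirubin, and nephritis on creatinine. Both rows lead to withholding or permanent discontinuation by grade.
- The diabetes/hyperglycemia row leads to withholding.
- The Grade 3-4 hyperthyroidism rule depends partly on laboratory tests.
- The second event of clinical interest in Section 17.2.2 is defined wholly by liver tests, "as determined by way of protocol-specified laboratory testing or unscheduled laboratory testing".
- Section 11.1 requires changes in CTCAE grade to be reported, laboratory values included.

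Safety is a secondary objective. If laboratory-defined events are not looked for on a schedule during early-stage maintenance, they could be under-recorded in the adverse event tables.

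**Working it through.** **Step 1: read the row cell by cell.** The row and the calendar header each split into 15 cells in both calendars.

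| Column | 10.1 labs | 10.1 AE review, exam, vital signs, ECOG, EBV PCR | 10.2 labs |
|---|---|---|---|
| Day 1 of Cycles 1, 2 and 4 | marked | marked | marked |
| Cycle 3 Day 1 | marked | marked, except EBV PCR | marked |
| Maintenance, first column (Cycles 5-12 or 5-16) | blank | marked | marked |
| Maintenance, Day 14-21 | blank | blank | blank |
| End of treatment | marked | marked | marked |
| Follow-up | marked | marked, except AE review | marked |

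The laboratory row's last two marks fall under end of treatment and follow-up, where they belong. The row has therefore not shifted sideways.

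**Step 2: look for another source of scheduled labs.**

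- Section 4.2 asks for closer blood count monitoring, but only in patients with hemophagocytic lymphohistiocytosis, and gives no schedule.
- The last column of Table 6 directs monitoring for some events, again without a visit schedule.
- Section 17.2.2 foresees unscheduled tests but does not require them.

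None of these schedules a draw in stage I-II maintenance.

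**Step 3: doses and time.** Maintenance doses: 12 - 5 + 1 = 8, which matches footnote 17. Eight cycles of 21 days are 168 days, about 5.5 months, in line with the stated 6 months. From Cycle 5 Day 1 to Cycle 12 Day 1 is 7 x 3 = 21 weeks. Scheduled draws before those doses: 0 of 8 in Section 10.1, against 8 of 8 for the same cycle numbers in Section 10.2.

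**Step 4: patients.** Section 14.0 expects 66% of 19 patients to have early-stage disease and assumes a complete response rate of 40%. Negative biopsy counts as complete response, and those are the patients who go on to maintenance.

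- Early stage: 0.66 x 19 = 12.5.
- Reaching maintenance: 12.54 x 0.40 = 5.0.
- Doses, if all eight are given: 5.0 x 8 = about 40.

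As a range, the plan's own 95% interval for the response rate is 0.18-0.62. This reproduces as 0.40 ± 1.96 x √(0.40 x 0.60 / 19) = 0.180 to 0.620. It gives 12.54 x 0.18 = 2.3 to 12.54 x 0.62 = 7.8 patients, or about 18 to 62 doses.

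**The case against.** The strongest objection is that everything rests on one blank cell in a table read from PDF. The neighbouring column holds garbled rotated text, and two other entries that Section 10.2 shows, the Day 1 label and the ±3 day window, are also blank in this column. This stands as a reason to check the source first. The alignment of the other rows makes a reading error less likely but does not exclude it. The missing window causes no gap of its own, because Section 9.3 and footnote 15 already give it.

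A second objection is that a blank cell does not mean no tests. In Section 10.2 the same row is blank after the SMILE cycles, so the calendars plainly do not list every draw. This stands in part. Section 9.4 leaves SMILE to institutional guidelines, whereas no such wording covers maintenance pembrolizumab. Still, Section 9.3 sets an order of events and does not limit testing. A reader might infer that these patients would be dosed with no laboratory testing at all. The documents support only that no testing is scheduled.

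Third, fewer rules depend on the labs than a count of Table 6 rows suggests. Hypothyroidism at Grades 2-4 and hyperthyroidism at Grade 2 are both managed with treatment continued, and both thyroid rows speak of signs and symptoms. The clear laboratory-triggered rules are liver, kidney and glucose. This stands.

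Four further inferences are tempting, and the documents do not carry them:

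- **A longer gap.** Counting from Cycle 4 Day 1 gives 31 to 39 weeks, but 10 to 17.6 of those weeks are the radiotherapy interval, when no pembrolizumab is given.
- **More patients.** Using the 5 of 7 responders in relapsed disease would count near-complete responses as complete.
- **Bias between stages.** Section 14.0 tabulates adverse events descriptively and separates the stages only for PFS and OS. No comparison of toxicity by stage is planned.
- **Missing thyroid tests in follow-up.** Follow-up is "standard clinic visit and laboratory tests (CBC, comp only"), and Section 11.8 lists "Decrease in function of the thyroid gland (if thyroid is in the ISRT field") as likely after radiotherapy. Both calendars state the same restriction, however, so there is no contradiction, and adding thyroid tests would be a preference.

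**Conclusion.** The point holds as an internal inconsistency, provided the source document shows the same blank cell. On the text available, eight stage I-II maintenance doses over 21 weeks have no protocol-scheduled hematology or chemistry, while the stage III-IV calendar schedules them at the same cycle numbers. The protocol's own liver, kidney and glucose rules, part of its hyperthyroidism rule, the hepatic event of clinical interest and the Section 11.1 reporting requirement all depend on such values.

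About 5 of 19 patients and 40 doses are affected (about 2 to 8 patients over the plan's own interval). This assumes the 66% and 40% figures, the same response rate in both stages as Section 14.0 assumes, and that patients receive all eight doses. The consequence is possible under-recording of laboratory-defined adverse events in this group. How much is lost depends on how often sites test without being told to, which the documents do not say.

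**What to change.** Check the Cycles 5-12 hematology/chemistry cell in Section 10.1 against the source document. If it is marked there, nothing further is needed on this row. If it is blank, the sponsor should reconcile the row for Cycles 5-12 with the Section 10.2 calendar, with the Table 6 rules and with Section 17.2.2, and should complete the column's blank day label in the same amendment. If the intended schedule is that of Section 10.2, coverage goes from 0 of 8 to 8 of 8 doses.

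Where patients have already had maintenance doses under this calendar, the safety report should say which laboratory results were actually obtained, so that an absence of events can be told apart from an absence of testing.

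The cost is one calendar amendment. Any added draws would fall at visits that already take place, with a few more values to enter.
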